8.3.3.3. Systemic Events

From Day 1 through Day 7, where Day 1 is the day of vaccination, participants' parent(s)/legal guardian will be asked to assess headache, fatigue, muscle pain, and joint pain and to record the symptoms in the e-diary in the evening. The symptoms will be assessed by the participant's parent(s)/legal guardian as mild, moderate, or severe according to the grading scale in Table 3. The parent(s)/legal guardian of a participant with a severe headache or severe joint pain will be prompted to contact the investigator to perform an unscheduled visit and assess the reaction. Participants' parent(s)/legal guardian will also be instructed to contact site staff if the participant experiences any possible Grade 4 prompted systemic event

(ie, emergency room visit or hospitalization for headache, fatigue, muscle pain, or joint pain) within 7 days after vaccination. Study staff may also contact the participant's parent(s)/legal guardian to obtain additional information on Grade 3 events entered into the e-diary.

Only an investigator is able to classify a participant's systemic event as Grade 4, after PE of the participant or documentation from another medically qualified source (eg, emergency room or hospital record) or telephone contact with the participant or participant's parent(s)/legal guardian. If a participant experiences a Grade 4 systemic event, the investigator must immediately notify the sponsor. The procedure for notification of the sponsor is provided in the study documentation.

If a systemic event persists beyond the end of the e-diary period following vaccination, the participant's parent(s)/legal guardian will be requested to report that information and/or any new AEs that develop to the investigator. The investigator will enter this additional information in the CRF.

Table 3. Systemic Event Grading Scale

	Grade 1 Mild	Grade 2 Moderate	Grade 3^a Severe	Grade 4^b
Fatigue (= tiredness in diaries)	Does not interfere with activity	Some interference with activity	Prevents daily activity ^c	Emergency room visit or hospitalization for severe fatigue
Headache	Does not interfere with activity	Some interference with activity	Prevents daily activity ^c	Emergency room visit or hospitalization for severe headache
Muscle pain	Does not interfere with activity	Some interference with activity	Prevents daily activity ^c	Emergency room visit or hospitalization for severe muscle pain
Joint pain	Does not interfere with activity	Some interference with activity	Prevents daily activity ^c	Emergency room visit or hospitalization for severe joint pain

- Participants experiencing \geq Grade 3 systemic events may be seen by the study site. Refer to the Unscheduled Visits section (Section 8.11) for further guidance.
- Grade 4 assessment should be made by the investigator. Grade 4 will not be collected in the diary but will be collected in the case report form.
- Prevents daily routine activity, ie, results in missed days of work or school or is otherwise incapacitating, or includes use of narcotics for analgesia.

8.3.3.4. Fever

In order to record information on fever, a digital thermometer will be given to the participant's parent(s)/legal guardian with instructions on how to measure the participant's oral temperature at home. Temperature will be collected in the evening daily for 7 days following vaccination (Days 1 through 7, where Day 1 is the day of vaccination) and at any time during the 7 days that fever is suspected. Fever is defined as an oral temperature of $\geq 100.4^{\circ}\text{F}$ ($\geq 38.0^{\circ}\text{C}$). The highest temperature for each day will be recorded in the e-diary. In the event of a fever on Day 7, temperature will be collected daily until the fever has resolved.

(1 day of temperature less than 100.4°F [38.0°C] in order to collect a stop date in the CRF). The parent(s)/legal guardian of a participant with a fever >104.0°F (>40.0°C) will be prompted to contact the investigator to assess the fever and perform an unscheduled visit as appropriate. Study staff must also contact the participant's parent(s)/legal guardian to obtain additional information if a temperature of ≥102.1°F (≥39.0°C) is entered into an e-diary. Temperature will be measured and recorded to 1 decimal place and then grouped into ranges for the analysis according to Table 4.

Table 4. Ranges for Fever

100.4°F to 101.1°F (≥38.0°C to 38.4°C)
101.2°F to 102.0°F (>38.4°C to 38.9°C)
102.1°F to 104.0°F (>38.9°C to 40.0°C)
>104.0°F (>40.0°C)

8.3.3.5. Use of Antipyretic/Pain Medication

From Day 1 through Day 7, where Day 1 is the day of vaccination, the participant's parent(s)/legal guardian will be asked to record the participant's use of antipyretic and/or pain medication used to treat symptoms reported in the e-diary in the evening.

8.3.4. Pregnancy Testing

Following screening, pregnancy tests may be urine or serum tests, but must have a sensitivity of at least 25 mIU/mL. This study will use urine tests for pregnancy screening. Pregnancy tests will be performed in all female participants ≥10 years of age at the times listed in the [SoA](#), immediately before the administration of each vaccine dose. A negative pregnancy test result will be required prior to the participant's receiving the study intervention. Pregnancy tests may also be repeated if requested by IRBs/ECs or if required by local regulations. In the case of a positive confirmed pregnancy, the participant will be withdrawn from administration of study intervention but may remain in the study.

8.3.5. Clinical Safety Laboratory Assessments

Clinical safety laboratory assessments will not be collected in this study.

8.4. Adverse Events, Serious Adverse Events, and Other Safety Reporting

The definitions of an AE and an SAE can be found in [Appendix 3](#).

The definitions of device-related safety events (ADEs and SADEs) can be found in [Section 10.6](#). Device deficiencies are covered in [Section 8.4.9](#).

AEs may arise from symptoms or other complaints reported to the investigator by the participant (or, when appropriate, by a caregiver, surrogate, or the participant's parent[s]/legal guardian), or they may arise from clinical findings of the investigator or other healthcare providers (clinical signs, test results, etc).

The investigator and any qualified designees are responsible for detecting, documenting, and recording events that meet the definition of an AE or SAE and remain responsible to pursue and obtain adequate information both to determine the outcome and to assess whether the event meets the criteria for classification as an SAE or caused the participant to discontinue the study intervention (see [Section 7.1](#)).

During the active collection period as described in Section 8.4.1, each participant/participant's parent(s)/legal guardian will be questioned about the occurrence of AEs in a nonleading manner.

In addition, the investigator may be requested by Pfizer Safety to obtain specific follow-up information in an expedited fashion.

8.4.1. Time Period and Frequency for Collecting AE and SAE Information

The time period for actively eliciting and collecting AEs and SAEs ("active collection period") for each participant begins from the time the participant/parent(s)/legal guardian provides informed consent, which is obtained before the participant's participation in the study (ie, before undergoing any study-related procedure and/or receiving study intervention), through and including a minimum of 1 month after each vaccination. NDCMCs and SAEs will be collected throughout the study.

Follow-up by the investigator continues throughout the active collection period and until the AE or SAE or its sequelae resolve or stabilize at a level acceptable to the investigator.

When a clinically important AE remains ongoing at the end of the active collection period, follow-up by the investigator continues until the AE or SAE or its sequelae resolve or stabilize at a level acceptable to the investigator and Pfizer concurs with that assessment.

For participants who are screen failures, the active collection period ends when screen failure status is determined.

If the participant or his or her parent(s)/legal guardian withdraws from the study and also withdraws consent for the collection of future information, the active collection period ends when consent is withdrawn.

If a participant permanently discontinues or temporarily discontinues study intervention because of an AE or SAE, the AE or SAE must be recorded on the CRF and the SAE reported using the Vaccine SAE Reporting Form.

Investigators are not obligated to actively seek information on AEs or SAEs after the participant has concluded study participation. However, if the investigator learns of any SAE, including a death, at any time after a participant has completed the study, and they consider the event to be reasonably related to the study intervention, the investigator must promptly report the SAE to Pfizer using the Vaccine SAE Reporting Form.

8.4.1.1. Reporting SAEs to Pfizer Safety

All SAEs occurring in a participant during the active collection period as described in [Section 8.4.1](#) are reported to Pfizer Safety on the Vaccine SAE Reporting Form immediately upon awareness and under no circumstance should this exceed 24 hours, as indicated in [Appendix 3](#). The investigator will submit any updated SAE data to the sponsor within 24 hours of its being available.

8.4.1.2. Recording Nonserious AEs and SAEs on the CRF

All nonserious AEs and SAEs occurring in a participant during the active collection period, which begins after obtaining informed consent as described in [Section 8.4.1](#), will be recorded on the AE section of the CRF.

The investigator is to record on the CRF all directly observed and all spontaneously reported AEs and SAEs reported by the participant.

As part of ongoing safety reviews conducted by the sponsor, any nonserious AE that is determined by the sponsor to be serious will be reported by the sponsor as an SAE. To assist in the determination of case seriousness, further information may be requested from the investigator to provide clarity and understanding of the event in the context of the clinical study.

8.4.2. Method of Detecting AEs and SAEs

The method of recording, evaluating, and assessing causality of AEs and SAEs and the procedures for completing and transmitting SAE reports are provided in [Appendix 3](#).

Care will be taken not to introduce bias when detecting AEs and/or SAEs. Open-ended and nonleading verbal questioning of the participant is the preferred method to inquire about AE occurrences.

8.4.3. Follow-Up of AEs and SAEs

After the initial AE or SAE report, the investigator is required to proactively follow each participant at subsequent visits/contacts. For each event, the investigator must pursue and obtain adequate information until resolution, stabilization, the event is otherwise explained, or the participant is lost to follow-up (as defined in [Section 7.3](#)).

In general, follow-up information will include a description of the event in sufficient detail to allow for a complete medical assessment of the case and independent determination of possible causality. Any information relevant to the event, such as concomitant medications and illnesses, must be provided. In the case of a participant death, a summary of available autopsy findings must be submitted as soon as possible to Pfizer Safety.

Further information on follow-up procedures is provided in [Appendix 3](#).

8.4.4. Regulatory Reporting Requirements for SAEs

Prompt notification by the investigator to the sponsor of an SAE is essential so that legal obligations and ethical responsibilities toward the safety of participants and the safety of a study intervention under clinical investigation are met.

The sponsor has a legal responsibility to notify both the local regulatory authority and other regulatory agencies about the safety of a study intervention under clinical investigation. The sponsor will comply with country-specific regulatory requirements relating to safety reporting to the regulatory authority, IRBs/ECs, and investigators.

Investigator safety reports must be prepared for SUSARs according to local regulatory requirements and sponsor policy and forwarded to investigators as necessary.

An investigator who receives SUSARs or other specific safety information (eg, summary or listing of SAEs) from the sponsor will review and then file it along with the SRSD(s) for the study and will notify the IRB/EC, if appropriate according to local requirements.

8.4.5. Environmental Exposure, Exposure During Pregnancy or Breastfeeding, and Occupational Exposure

Environmental exposure occurs when a person not enrolled in the study as a participant receives unplanned direct contact with or exposure to the study intervention. Such exposure may or may not lead to the occurrence of an AE or SAE. Persons at risk for environmental exposure include healthcare providers, family members, and others who may be exposed. An environmental exposure may include EDP, EDB, and occupational exposure.

Any such exposures to the study intervention under study are reportable to Pfizer Safety within 24 hours of investigator awareness.

8.4.5.1. Exposure During Pregnancy

An EDP occurs if:

- A female participant is found to be pregnant while receiving or after discontinuing study intervention.
- A male participant who is receiving or has discontinued study intervention inseminates a female partner.
- A female nonparticipant is found to be pregnant while being exposed or having been exposed to study intervention because of environmental exposure. Below are examples of environmental EDP:
 - A female family member or healthcare provider reports that she is pregnant after having been exposed to the study intervention by injection, inhalation or skin contact.

- A male family member or healthcare provider who has been exposed to the study intervention by injection, inhalation or skin contact then inseminates his female partner prior to or around the time of conception.

The investigator must report EDP to Pfizer Safety within 24 hours of the investigator's awareness, irrespective of whether an SAE has occurred. The initial information submitted should include the anticipated date of delivery (see below for information related to termination of pregnancy).

- If EDP occurs in a participant/participant's partner, the investigator must report this information to Pfizer Safety on the Vaccine SAE Reporting Form and an EDP Supplemental Form, regardless of whether an SAE has occurred. Details of the pregnancy will be collected after the start of study intervention and until the participant's last visit in the study.
- If EDP occurs in the setting of environmental exposure, the investigator must report information to Pfizer Safety using the Vaccine SAE Reporting Form and EDP Supplemental Form. Since the exposure information does not pertain to the participant enrolled in the study, the information is not recorded on a CRF; however, a copy of the completed Vaccine SAE Reporting Form is maintained in the investigator site file.

Follow-up is conducted to obtain general information on the pregnancy and its outcome for all EDP reports with an unknown outcome. The investigator will follow the pregnancy until completion (or until pregnancy termination) and notify Pfizer Safety of the outcome as a follow-up to the initial EDP Supplemental Form. In the case of a live birth, the structural integrity of the neonate can be assessed at the time of birth. In the event of a termination, the reason(s) for termination should be specified and, if clinically possible, the structural integrity of the terminated fetus should be assessed by gross visual inspection (unless preprocedure test findings are conclusive for a congenital anomaly and the findings are reported).

Abnormal pregnancy outcomes are considered SAEs. If the outcome of the pregnancy meets the criteria for an SAE (ie, ectopic pregnancy, spontaneous abortion, intrauterine fetal demise, neonatal death, or congenital anomaly), the investigator should follow the procedures for reporting SAEs. Additional information about pregnancy outcomes that are reported to Pfizer Safety as SAEs follows:

- Spontaneous abortion including miscarriage and missed abortion should be reported as an SAE;
- Neonatal deaths that occur within 1 month of birth should be reported, without regard to causality, as SAEs. In addition, infant deaths after 1 month should be reported as SAEs when the investigator assesses the infant death as related or possibly related to exposure to the study intervention.

Additional information regarding the EDP may be requested by the sponsor. Further follow-up of birth outcomes will be handled on a case-by-case basis (eg, follow-up on preterm infants to identify developmental delays). In the case of paternal exposure, the investigator will provide the participant with the Pregnant Partner Release of Information Form to deliver to his partner. The investigator must document in the source documents that the participant was given the Pregnant Partner Release of Information Form to provide to his partner.

For a female participant who becomes pregnant, this information will be shared with the study participant's parent(s)/legal guardian if the participant's age is in accordance with local/country regulations.

8.4.5.2. Exposure During Breastfeeding

An EDB occurs if:

- A female participant is found to be breastfeeding while receiving or after discontinuing study intervention.
- A female nonparticipant is found to be breastfeeding while being exposed or having been exposed to study intervention (ie, environmental exposure). An example of environmental EDB is a female family member or healthcare provider who reports that she is breastfeeding after having been exposed to the study intervention by injection, inhalation or skin contact.

The investigator must report EDB to Pfizer Safety within 24 hours of the investigator's awareness, irrespective of whether an SAE has occurred. The information must be reported using the Vaccine SAE Reporting Form. When EDB occurs in the setting of environmental exposure, the exposure information does not pertain to the participant enrolled in the study, so the information is not recorded on a CRF. However, a copy of the completed Vaccine SAE Reporting Form is maintained in the investigator site file.

An EDB report is not created when a Pfizer drug specifically approved for use in breastfeeding women (eg, vitamins) is administered in accordance with authorized use. However, if the infant experiences an SAE associated with such a drug, the SAE is reported together with the EDB.

8.4.5.3. Occupational Exposure

The investigator must report any instance of occupational exposure to Pfizer Safety within 24 hours of the investigator's awareness using the Vaccine SAE Reporting Form, regardless of whether there is an associated SAE. Since the information about the occupational exposure does not pertain to a participant enrolled in the study, the information is not recorded on a CRF; however, a copy of the completed Vaccine SAE Reporting Form must be maintained in the investigator site file.

8.4.6. Cardiovascular and Death Events

Not applicable.

8.4.7. Disease-Related Events and/or Disease-Related Outcomes Not Qualifying as AEs or SAEs

Not applicable.

8.4.8. Adverse Events of Special Interest

AESIs are examined as part of routine safety data review procedures throughout the clinical trial and as part of signal detection processes. Should an aggregate analysis indicate that these prespecified events occur more frequently than expected, eg, based on epidemiological data, literature, or other data, then this will be submitted and reported in accordance with Pfizer's safety reporting requirements. Aggregate analyses of safety data will be performed on a regular basis per internal SOPs.

For this study, there are no AESIs related to known pharmacology, toxicology, class effects, published literature, or previously identified signals in the product development program safety database. However, because this study does not include active surveillance for LD, diagnosis terms under the ICD-10 code for LD (A69.2) that represent clinical diagnoses of acute LD (early, early disseminated, or late manifestations) made by a qualified healthcare provider will be considered AESIs for this study. The purpose of specifying these conditions as AESIs is to help ensure thorough accounting of incident LD occurring throughout the study.

All AESIs must be reported as an AE or SAE following the procedures described in Sections 8.4.1 through 8.4.4. An AESI is to be recorded as an AE or SAE on the CRF. In addition, an AESI that is also an SAE must be reported using the Vaccine SAE Reporting Form.

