Review e-diary data (daily review is optimal during the active diary period) ^c	X	X	X			X		
Review ongoing e-diary symptoms and obtain stop dates ^c		X	X	X			X	

Visit Number	1	2	3	4	5	6	7	8
Visit Identifier ^a	Month 0 Dose 1 (Start of Primary Series)	Month 2 Dose 2	Month 6 Dose 3 (End of Primary Series)	Month 7	Month 12 Telephone Call	Month 18 Booster Dose	Month 19	Month 24 Telephone Call
Visit Window ^b	Day 1	50-70 Days After Visit 1	172-192 Days After Visit 1	28-42 Days After Visit 3	355-375 Days After Visit 1	535-555 Days After Visit 1	28-42 Days After Visit 6	172-192 Days After Visit 6
Collect AEs, NDCMCs, and SAEs as appropriate ^f	X	X	X	X	X	X	X	X
Collect e-diary (or assist with deletion of app at final site visit) ^e				X			X	

- a. If approved by the sponsor, visits may take place at the investigator's site or an alternate site location approved by the investigator.
- b. Day relative to the start of study intervention (Day 1).
- c. Including, if indicated, a PE.
- d. If a participant is withdrawn, the investigator should request that the participant return for 1 final visit to perform the safety-related procedures as indicated for the next scheduled study visit. A final telephone contact visit ~6 months after the last vaccination preceding withdrawal should be performed. See [Section 7.2](#) for details.
- e. Provide instructions on e-diary completion and ask the participant's parent(s)/legal guardian to complete the e-diary each day from Day 1 through Day 7, with Day 1 being the day of vaccination. E-diaries will be returned in person at Visits 4 and 7 (ie, after Dose 3 and after the booster dose, respectively).
- f. AEs (nonserious) and SAEs will be collected from the time informed consent is obtained through and including a minimum of 1 month after each vaccination. NDCMCs and SAEs will be collected throughout the study.

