10.3.1. Definition of AE

AE Definition

An AE is any untoward medical occurrence in a patient or clinical study participant, temporally associated with the use of study intervention, whether or not considered related to the study intervention.Note: An AE can therefore be any unfavorable and unintended sign (including an abnormal laboratory finding), symptom, or disease (new or exacerbated) temporally associated with the use of study intervention.

Events Meeting the AE Definition

Any abnormal laboratory test results (hematology, clinical chemistry, or urinalysis) or other safety assessments (eg, ECG, radiological scans, vital sign measurements), including those that worsen from baseline, considered clinically significant in the medical and scientific judgment of the investigator. Any abnormal laboratory test results that meet any of the conditions below must be recorded as an AE:
Is associated with accompanying symptoms.Requires additional diagnostic testing or medical/surgical intervention.Leads to a change in study dosing (outside of any protocol-specified dose adjustments) or discontinuation from the study, significant additional concomitant drug treatment, or other therapy.Exacerbation of a chronic or intermittent preexisting condition, including an increase in either frequency and/or intensity of the condition.New condition detected or diagnosed after study intervention administration, even though it may have been present before the start of the study.Signs, symptoms, or the clinical sequelae of a suspected drug-drug interaction.Signs, symptoms, or the clinical sequelae of a suspected overdose of either study intervention or a concomitant medication. Overdose per se will not be reported as an AE or SAE unless it is an intentional overdose taken with possible suicidal/self-harming intent. Such overdoses should be reported regardless of sequelae.

Events **NOT** Meeting the AE Definition

- Any clinically significant abnormal laboratory findings or other abnormal safety assessments that are associated with the underlying disease, unless judged by the investigator to be more severe than expected for the participant's condition.
- The disease/disorder being studied or expected progression, signs, or symptoms of the disease/disorder being studied, unless more severe than expected for the participant's condition.

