3.1.1.3. Adverse Events and Serious Adverse Events

Standard algorithms for handling missing AE dates and missing AE severity will be applied as described in the Pfizer vaccine data standard rules. Completely missing AE start dates will not be imputed.

The following derivations (yes/no) will be included for each participant:

- Any AE reported within 30 days (Day 1 through Day 31) after each dose and after any dose
- Any related AE reported within 30 days (Day 1 through Day 31) after each dose and after any dose
- Any immediate AE (AE start time is within 30 minutes after vaccination) reported after each dose and after any dose
- Any severe AE reported within 30 days (Day 1 through Day 31) after any dose
- Any AE leading to study withdrawal after the first dose
- Any AE leading to death after the first dose

AE reports will exclude any reactogenicity events (but not exclude reactogenicity SAEs) reported in the AE CRF during the e-diary collection period.

- Any AESI reported during the study after the first dose

Because this study does not include active surveillance for LD, diagnosis terms under the ICD-10 code for LD (A69.2) that represent clinical diagnoses of acute LD (early, early disseminated, or late manifestations) made by a qualified healthcare provider will be considered AESIs for this study. The AESI PTs will be included in the data handling memo before the database lock.

- NDCMCs reported during the study after the first dose
- SAEs reported during the study after the first dose (including reactogenicity events reported in the AE CRF during the e-diary collection period)
- Related SAEs reported during the study after the first dose (including reactogenicity events reported in the AE CRF during the e-diary collection period)

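### Lyme disease is made an AESI so that cases are counted throughout the study, but for most of follow-up the protocol states no active collection of nonserious cases

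*Protocol*

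**What the plan says.** Protocol Section 8.4.8 classes clinical diagnoses of acute Lyme disease (LD), early through late, as AESIs. The reason given is "because this study does not include active surveillance for LD", and the aim is stated outright: "The purpose of specifying these conditions as AESIs is to help ensure thorough accounting of incident LD occurring throughout the study". On mechanics it says: "All AESIs must be reported as an AE or SAE following the procedures described in Sections 8.4.1 through 8.4.4".

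Section 8.4.1 sets the active collection period from consent "through and including a minimum of 1 month after each vaccination. NDCMCs and SAEs will be collected throughout the study". Footnote f of the Schedule of Activities agrees: "AEs (nonserious) and SAEs will be collected from the time informed consent is obtained through and including a minimum of 1 month after each vaccination". It too names only NDCMCs and SAEs as collected for the whole study. Protocol Section 4.1 and SAP Section 2.3 make the same split, there without the word minimum. None of these four places mentions AESIs.

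SAP Section 3.1.1.3 limits the general AE derivations to Day 1 through Day 31 after a dose but derives "Any AESI reported during the study after the first dose".

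**The concern.** The stated purpose and the stated collection rule do not match. An LD diagnosis need not be serious, and Section 8.4.8 expressly includes early disease. Nor does it obviously meet the NDCMC test in Section 10.3.2, which requires a lifelong, incurable condition. A nonserious case between post-dose windows therefore falls under the general AE rule, and no passage says that families will be asked about it.

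The AESI table would cover the whole study by its definition and could be read as LD incidence over about 24 months. Its completeness outside the post-dose periods would depend on how each site read the protocol. Section 8.4.8 also foresees comparing AESI frequency with what is expected from, for example, epidemiological data. An incomplete numerator would pull the observed side of that comparison down.

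**Working it through.** **Inputs**
- Visit windows (Schedule of Activities), as days after Visit 1: Dose 2 at 50-70 (midpoint 60), Dose 3 at 172-192 (midpoint 182), booster at 535-555 (midpoint 545).
- Final call: 172-192 days after the booster (midpoint 182).
- Visits 4 and 7: 28-42 days (midpoint 35) after Dose 3 and after the booster.
- AE window in the SAP: Day 1 through Day 31, which is 31 days per dose.

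**The plan's own figure.** Follow-up = 545 + 182 = 727 days, or 23.9 months. The extremes are 535 + 172 = 707 and 555 + 192 = 747 days (23.2 to 24.5 months). This agrees with the stated duration of about 24 months.

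**Literal reading: one window per dose.**
- Covered: 4 × 31 = 124 days; 124/727 = 17%.
- Gap after Dose 1: 60 − 31 = 29 days.
- Gap after Dose 2: 182 − 60 − 31 = 91 days.
- Gap after Dose 3: 545 − 182 − 31 = 332 days.
- Gap after the booster: 727 − 545 − 31 = 151 days.
- Total uncovered: 29 + 91 + 332 + 151 = 603 days; 603/727 = 83%.
- Windows of 28 to 42 days instead: (4 × 28)/747 = 15% to (4 × 42)/707 = 24% covered.

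**Generous reading.** One month is a minimum, so suppose that AEs are collected without a break from Dose 1 to Visit 4 and from the booster to Visit 7.
- Midpoints: 182 + 35 + 35 = 252 days; 252/727 = 35% covered.
- Low end: (172 + 28 + 28)/747 = 228/747 = 31% covered, 69% not.
- High end: (192 + 42 + 42)/707 = 276/707 = 39% covered, 61% not.

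On both readings most follow-up time lies outside the stated period.

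**Why a share of time is not a share of cases.** The documents give no monthly LD rates. As an assumption, take a yearly season of 3 to 6 months starting on any calendar day relative to Dose 1. The 31-day windows then cover 0 to 34% of in-season follow-up (average 17%). The generous reading covers 0 to 69% (average 35%) and exceeds half for about 19% of season start dates. The fraction of cases inside the windows thus depends on enrolment timing, which the documents do not give.

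**Does another passage close the gap?** Section 8.4 ties questioning about AEs to the active collection period, and Section 8.4.1.2 ties CRF recording to the same period. The Month 12 and Month 24 call procedures (Sections 8.10.5 and 8.10.8) list AEs but refer back to Section 8.4. The AE row of the Schedule of Activities is marked at all eight contacts, but only as appropriate and subject to footnote f.

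**The case against.** The best defence is that the specific rule governs the general one. Section 8.4.8 makes AESI reporting mandatory, sets no time limit and states a whole-study purpose. The visit instructions refer to Section 8.4, which contains Section 8.4.8. There are also practical routes to a diagnosis:
- Spontaneously reported AEs go on the CRF (Section 8.4.1.2).
- Serious LD is collected throughout.
- At Visits 1 to 7 families are asked to call about significant illness.
- Eligibility is rechecked at Visits 2 to 7, and recent or disseminated LD is an exclusion criterion.
- SAP Section 6.4.3 lists medications for AEs, including LD.

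Much of this stands. A reader might infer that most Lyme diagnoses will never be recorded; the documents do not support that. The intent is plainly whole-study capture, and sites may well record cases at any contact.

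The gap remains because none of these routes is a stated question about LD. Spontaneous reports depend on the family volunteering the event. The eligibility look-back is 3 months for nondisseminated LD, and there is no eligibility check at the Month 24 call, which closes the 151-day gap. Section 6.9 records medications to treat AEs, so it is no independent source for a case not recorded as an AE.

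A reader might also infer that Appendix 3 removes LD from the AE definition, since its list of non-AEs includes "The disease/disorder being studied or expected progression, signs, or symptoms of the disease/disorder being studied". That is weak. Section 8.4.7, on disease-related events that do not qualify as AEs, is marked not applicable. Section 8.4.8 requires LD to be recorded, and the bullet speaks of severity relative to a condition the participant already has. A clarifying note is optional.

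**Conclusion.** The point holds as an inconsistency between purpose and procedure. Followed literally, the collection rule gives no stated elicitation of nonserious LD for about 83% of follow-up at nominal visit times with 31-day windows, or about 61 to 69% on the generous reading. In that time capture rests on spontaneous reports, incidental detection at visits and site interpretation, so it may be incomplete and may vary between sites.

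These figures are shares of time. The number or share of diagnoses lost cannot be computed from the documents.

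Two limits apply. LD is not one of the five primary safety endpoints, so these are not directly affected. A reader might also expect a bias between arms, but both arms share the same windows under blinded, site-based randomization within age strata, and no differential effect is shown.

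**What to change.** 1. In Protocol Sections 4.1 and 8.4.1 and in footnote f of the Schedule of Activities, add AESIs to the event types collected for the whole study. Align the matching sentence in SAP Section 2.3.
2. At existing contacts, including the Month 12 and Month 24 calls, ask whether a healthcare provider has diagnosed Lyme disease since the last contact, and record any such diagnosis.
3. Optionally, note in Section 10.3.1 that the bullet on the disease being studied does not exclude incident Lyme disease.
4. SAP version 3 (01 Aug 2025) still cites the original protocol of 25 Jul 2022, so some participants may already be past these contacts. For them, footnote the AESI table: nonserious cases were actively elicited only during the post-dose collection periods, and other cases reflect spontaneous or incidental reports. Relabelling the endpoint as cases within 1 month of a dose or serious would be wrong, because the table can also hold nonserious cases reported between windows.

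The cost is protocol wording, a CRF completion instruction, a table footnote and a few extra AE records. No visit is added.
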